### Research Question and Aims

**Hypothesis:** Our overarching hypothesis is that multilevel interventions for patient, parent, and practice can enhance provider recommendations for HPV vaccination.

**Aims, purpose, or objectives:** We are testing this hypothesis through three phases for which we have developed three protocols. In this third phase, with this protocol, we have three primary aims.

**Aim 1:** Test the hypothesis that, as compared to no intervention, a practice-level intervention utilizing reminder-recalls featuring the availability of non-medication and medication anesthetics, the convenience of nurse-only visits, and the use of persuasive language for early, on-time vaccinations—“Less Pain, Less Fuss, Right Now!”—will improve the odds of a child receiving an HPV vaccine dose by at least 20%.

**Aim 2:** Test the hypothesis that, as compared to no intervention, a provider-level intervention utilizing missed opportunities audit-and-feedback and equipping providers with a strong-recommendation toolkit—“Make It Count!”—will improve the odds of a child receiving an HPV vaccine dose by at least 20%.

**Aim 3:** Test the hypothesis that simultaneous implementation of interventions targeting individual, interpersonal, and organizational factors will have a synergistic effect more than doubling the odds of a child receiving an HPV vaccine dose.

**Background:** Our relevant experience includes our team’s considerable work in vaccine delivery research with particular emphasis on HPV vaccination. This work has focused on parental attitudes toward HPV vaccination, population knowledge and attitudes about HPV vaccination, awareness and knowledge of HPV vaccination among uninsured, low-income populations; factors associated with HPV vaccination initiation and completion, and strategies to address vaccine hesitancy. We have also studied population health interventions that health care organizations can adopt including reminder-recall strategies and others. Our research team partners closely with primary care practice leadership to identify priorities for research to improve the clinical practice and community health. The clinical sites involved in this effort serve as a laboratory for health care delivery research, and our team has significant experience conducting research in these clinics. (See attachments 1, 2, and 3 for letters of support.)

Current knowledge suffers significant gaps. Nearly 39,000 human papillomavirus (HPV)–associated cancers occur each year including 23,000 in females and 16,000 in males. Of these, 30,700 result from HPV infection, and 28,500 result from HPV strains preventable by the highly immunogenic and efficacious 9-valent HPV vaccine. While HPV vaccination is recommended routinely for all males and females 11 to 12 years of age, HPV vaccination rates in the United States (US) are failing to reach national goals; thus, leaving millions at risk for HPV-associated cancer. Rates of HPV vaccine series completion are significantly lower than rates observed for the other two adolescent vaccines introduced at approximately the same time for the same age group. The HPV vaccination rates in our community and region reflect the low rates observed in Minnesota and the rest of the US. Barriers to vaccination reported by parents of adolescents who have not started or completed the series include the beliefs that the vaccine is optional, not recommended, unnecessary, and unsafe. Because the vaccine series has involved three injections over six months in the past, the series required several visits. However, adolescents infrequently use health services; thus, they lack frequent opportunities for vaccination. Educational campaigns

have failed to produce substantial improvements in HPV vaccine delivery rates. While other countries have addressed HPV vaccine delivery successfully through school-based programs, the US relies on primary-care-practice delivery of routine adolescent vaccination. Other vaccines in the US have achieved desired national goals in large part through state-based school vaccine mandates, but states have avoided mandating HPV vaccine for school attendance because of political concerns. By contrast, several proven practice-level interventions offer small but incremental improvements in HPV vaccine delivery rates. Reminder-recalls directed to the patients and their parents are such practice-level interventions. They have produced varying effect sizes with improving HPV vaccination rates. Tailoring the message to address both patient and parent issues with HPV vaccination offers an opportunity to improve the effect size, but this has not been tested directly. Other innovative practice-level strategies make sense in theory but have not been tested empirically—such as routinely offering medication anesthetics to make the HPV vaccination relatively painless and emphasizing nurse visits (not requiring a clinician encounter) with the nurse utilizing standing orders (or nursing protocols) to facilitate easy access.

Our preliminary data supports our work. Using patient-level data geocode-matched to publically available data from the American Community Survey, we characterized HPV vaccination initiation and completion rates in our local population. We observed a greater likelihood of vaccination among females and older adolescents. We also found our composite, environmental level measure of socioeconomic status to be significantly associated with both initiation and completion, even after controlling for individual level variables known to be associated with vaccination. Across a 7-county area in southeast MN where we have sufficient population coverage to ascertain population estimates we found 4,066 (27.1%) of children and adolescents aged 9 to 14 had received one or more doses of HPV vaccine, and 1,524 (10.1%) of those of the same age had received three or more doses of HPV vaccine. Receipt of one or more doses of HPV vaccine ranged from 11.7% to 33.8% across counties. Receipt of the three doses needed to complete the series ranged from 2.5% to 13.7%. These rates are like the rest of Minnesota and the overall US population. None of the rates approximated the 80% Healthy People 2020 goal.

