### Statistical Analysis Plan

**Power Statement:** Stepped-wedge cluster randomization trials typically have more statistical power than other cluster randomized designs, because each cluster is able to serve as its own control, accounting directly for the within cluster correlation of outcomes. Because of the complex nature of the design, we estimate statistical power using simulation, which accounted for potential differences in baseline rates across sites. Based on pilot data from a 12-month period, we assumed an average cluster size of 800 children (400 males and 400 females), a baseline probability of requiring any vaccination of 25% (log-odds of -1.1), and a conservative estimate of the standard deviation of the random effect of 0.5, assuming a secular treatment effect. These estimates are conservative. We have sufficient power to detect meaningful patient-centered and provider-level effects in both the sex-stratified and full cohorts. For the interaction between patient-centered and provider-level effects (with the same assumptions described above), based on the simulation, we have at least 80% power to detect an odds ratio (OR) of 1.5 or greater when looking at males and females separately and of 1.34 or greater in the full cohort. To aid in interpretation, an OR of 1.34 means that a significant interaction would be detected if the synergistic effect of the two treatments or interventions is 1.34 times higher than the product of the individual ORs. For example, with ORs of 1.28 for both interventions individually, we can detect a synergistic effect of 2.2. Although our power estimates are conservative, power is somewhat marginal (70% to detect an OR of 1.45) for the synergistic effect in the sex-stratified cohorts; however, we have sufficient power to detect an effect using the combined sample. We conducted several sensitivity analyses adjusting the terms in our model (baseline probability, random effect standard deviation and secular trend) and found small changes in our already conservative power estimates. We used average cluster instead of actual size which was reasonable given our pilot data indicate only a slight imbalance across the clusters. Our average observed total cluster size was 895, with close to 50% male and 50% female; we assumed an average cluster size of 800 (400 for each sex) to allow for decreases in eligible participants overtime as a result of the effect of our interventions.

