**Data Analysis Plan:** We will summarize patient characteristics (including sex, age, and race/ethnicity, by intervention status (usual care, parent reminder-recall letters, provider audit-feedback reports, and combination of parent reminder-recall letters, provider audit-feedback reports). All patients will be analyzed on an intention to treat status; this principle will be extended to the practice status, so that delays in implementation of an intervention will not affect the intervention status of patients. We will use generalized linear mixed models to assess the effects of the interventions. All models will be assessed both overall and stratified by sex in recognition of differential rates of HPV vaccination among males and females. Our main model will be a mixed effects logistic regression model which will allow us to test the three primary aims.

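### Does powering only the interaction odds ratio leave the doubling in Aim 3 untested?

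*Protocol*

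**What the plan says.** In the protocol's Research Question and Aims, Aim 3 is to test the hypothesis that implementing both interventions at once "will have a synergistic effect more than doubling the odds of a child receiving an HPV vaccine dose". Aims 1 and 2 have the same form: each intervention alone "will improve the odds of a child receiving an HPV vaccine dose by at least 20" per cent. The Methods and Study Design paragraphs say that the factorial layout lets one trial evaluate each intervention by itself and the two together.

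The SAP's Data Analysis Plan names a "mixed effects logistic regression model which will allow us to test the three primary aims". It does not say which coefficient or contrast answers which aim.

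For the combination, the Power Statement gives at least 80% power for an interaction OR of 1.34 in the full cohort and 1.5 within each sex. It explains that "a significant interaction would be detected if the synergistic effect of the two treatments or interventions is 1.34 times higher than the product", meaning the two single-intervention ORs multiplied together, and then gives an example: "with ORs of 1.28 for both interventions individually, we can detect a synergistic effect of 2.2". Later it says that "power is somewhat marginal (70% to detect an OR of 1.45) for the synergistic effect in the sex-stratified cohorts".

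**The concern.** Read literally, Aim 3 makes two statements: the interventions reinforce each other (interaction OR above 1), and together they more than double the odds (combined OR above 2). The Power Statement addresses only the first. The SAP does not name the contrast that decides Aim 3, and it does not say that the combined OR will be reported with a confidence interval. It also uses the term synergistic effect for two quantities: the combined OR in the 2.2 example and the interaction OR in the 1.45 figure.

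Aim 3 is a primary aim. If a significant interaction were reported as confirming the whole of it, the doubling would be claimed without having been examined.

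**Working it through.** **Inputs.** From the Power Statement: 800 children per practice and step (400 per sex), baseline probability 25%, practice random-effect SD 0.5, single ORs 1.28, interaction OR 1.34. From the Allocation table: six practices, four steps, 24 cells. From Aims 1 and 2: single ORs of at least 1.2. Assumed because not stated: two-sided alpha 0.05. The form of the time term is also not given, so three were tried.

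**The SAP's example.** Combined OR = OR1 x OR2 x interaction OR = 1.28 x 1.28 x 1.34 = 2.195, which rounds to the stated 2.2.

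**The SAP's power.** Standard errors (SE) come from generalised least squares for a random-intercept logistic model on the 24 cells, averaged over draws of the practice effects. Power against 1 is Φ(ln OR / SE − 1.96).

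- With categorical steps and 800 per cell, SE(b12) = 0.103. Then ln 1.34 / 0.103 = 0.2927 / 0.103 = 2.84, and power is about 81% (stated: at least 80%).
- With 400 per cell, SE(b12) = 0.1456. Power is about 79.5% at 1.5 (stated: at least 80%) and about 72% at 1.45 (stated: 70%).

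The stated figures are therefore tests of the interaction against 1, and they are not in dispute.

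**Does a significant interaction imply doubling?** No.

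- Single ORs 1.2, interaction 1.34: 1.2 x 1.2 x 1.34 = 1.93, below 2, while interaction power is still about 80%.
- At an interaction of 1.34, both single ORs must reach √(2/1.34) = 1.22 for the combined OR to be 2.
- Conversely, single ORs of 1.42 with no interaction give 1.42 x 1.42 = 2.02, a doubling that the interaction test is not built to find.

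**If 2 were a null value.** The log combined OR is b1 + b2 + b12, with ln 2.195 = 0.786 and ln 2 = 0.693. The probability that the lower 95% limit exceeds 2 is Φ((0.786 − 0.693)/SE − 1.96).

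| Time term | Interaction power at 1.34 | SE(b1+b2+b12) | P(lower limit > 2) |
|---|---|---|---|
| Categorical steps | 80.9% | 0.1215 | 11.7% |
| Linear | 98.5% | 0.121 | 11.8% |
| None | 98.5% | 0.0405 | 63.5% |

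Of the three, only categorical steps reproduce the SAP's 80%. With them the expected interval is exp(0.786 ± 1.96 x 0.1215) = 1.73 to 2.79. The estimate falls below 2 in about 22% of trials, and a true combined OR of about 2.8 is needed for the lower limit to exceed 2 in about 80% of trials. Power for the combined OR against 1 exceeds 99.9%.

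**Same form in Aims 1 and 2.** At a single OR of 1.28, SE(b1) = 0.089. Power against 1 is about 79%, while the lower limit exceeds 1.2 in about 11% of trials.

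**The case for a change.** The strongest case for a change is that the aim is worded as a hypothesis to be tested, not as a forecast. A statistical plan exists to fix the deciding quantity before data are seen, and this one names none for Aim 3. The 2.2 is an illustration conditional on 1.28 for each intervention. Naming the interaction OR as the test and reporting the combined OR with its interval would cost a sentence and one contrast.

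Part of this stands. A significant interaction is neither sufficient nor necessary for a doubling, and the contrast is not written down.

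The rest is weaker. The Power Statement speaks of detecting a significant interaction and defines it as a ratio to the product of the single ORs, so the intended test is clear. Its example is the link to the aim's wording: the detectable interaction, with plausible single effects, yields just over 2. Aims 1 and 2 pair a percentage with the hypothesis in the same way, and nothing suggests that 1.2 is a null value there. The 12% is thus the power of a test that nobody proposed. The double use of synergistic effect is settled by context, since 2.2 and 1.45 cannot be mistaken for each other.

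**Conclusion.** No change is needed. The interaction test is a valid test of synergy, and its stated power reproduces. The combined OR against usual care is the sum of three coefficients of the planned model (one coefficient under four-level coding), so its estimate and interval need no new data, model or design. The protocol already says that the combination will be assessed, and an analyst would report it alongside the interaction.

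No stated figure or rule is wrong, and following the plan gives sound estimates. Requiring a lower limit above 2 would be a debatable choice, not a correction. The real point is one of interpretation: a significant interaction alone should not be read as a proven doubling, and neither document says that it will be.

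The 12% holds only if 2 is taken as a null value, alpha is 0.05 two-sided and time is adjusted for; with no time term it is about 63%. All figures are normal approximations without a small-sample correction for six practices.

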## Study Design and Methods

### Methods:

The overall study grant of which this protocol is the third of three parts is designed as a stepped wedge cluster randomized trial. The cluster approach prevents cross-contamination between patients or between providers as we allocate two separate interventions (i.e. “Less Pain, Less Fuss, Right Now!” and “Make It Count!”) — to the six primary care practices. The stepped-wedge design permits us to test the presence of each of the interventions in each primary care practice, making trial participation more attractive to each primary care practice, while also allowing each practice to serve as its own control, reducing the bias due to imbalanced risk factors across practices. The incorporation of a factorial design allows us to use a single trial to test two interventions and assess each individually and in combination. The design also provides opportunity to conserve overall sample size while maintaining power.

**Research Setting:** We will conduct our study in six primary care practices (Community Pediatric and Adolescent Medicine, Family Medicine, Northeast Family Clinic, Northwest Family Clinic, Southeast Family Clinic, and Kasson Clinic) that have expressed a commitment to improving HPV vaccination rates. These practices employ salaried nurse-practitioners, pediatricians, and family physicians. Two of the practices train residents in family medicine and pediatrics. The study sites provide care to children including those in the target age group, 11 to 12 years of age. Five of the primary care practices are in Rochester, Minnesota and one of the practices is 15.7 miles west of Rochester in Kasson, Minnesota. Uniformity across the six clinical practices will enhance the success and efficiency of the study and contribute to the fidelity of the interventions as well as the interpretability of the results. None of the practices have had or currently have campaigns in place to reduce pain of HPV vaccination, although nurses do have access to an instant topical anesthetic skin refrigerant or vapo-coolant (Gebauer's Pain Ease Mist Spray®, Gebauer Co.) that does not require a provider order and have been taught comfort holds for infants receiving vaccinations. None have a reminder-recall process in place for HPV vaccination. None have provider-performance assessments regarding HPV vaccination. All six practices ask patients receiving HPV vaccine to wait 15 minutes post vaccination to identify symptoms of syncope and utilize the same protocol for timing the 15 minutes.

**Study Design:** To accomplish Aims 1-3, we will use a stepped-wedge cluster randomized trial with process evaluation. The cluster approach prevents cross-contamination between patients or providers as we allocate two separate interventions to the six primary care practices. The stepped-wedge design permits us to test the presence of each of the interventions in each

NCI HPV R01 Protocol

Co-PIs: [name], & [name]

Mayo Clinic – R01CA217889

primary care practice, making trial participation more attractive to each primary care practice, while also allowing each practice to serve as its own control, reducing the bias due to imbalanced risk factors across practices. The incorporation of a factorial design allows us to use a single trial to test two interventions and assess each individually and in combination. The design also provides opportunity to conserve sample size while maintaining power.

**Allocation:** We will allocate participating practices as illustrated in the table. There will be four 12-month steps in our design, for a total of 48 months. The first step will be a baseline period in which no intervention is implemented; data collected during this period will provide a within-practice control group for each practice. For the next step, two practices will be randomly selected to receive intervention 1 (Aim 1) and two practices randomly selected to receive intervention 2 (Aim 2). For the third step, the two practices with no intervention will be randomly allocated to 1 or 2; practices initially with intervention 1 will be randomly allocated to interventions 1+2 or intervention 1; and practices initially with intervention 2 will be randomly allocated to interventions 1+2 or 2. For the final step, all practices will receive both interventions. To ensure balance of patient numbers across interventions, we will block randomize at the first step, with the six practices grouped into three pairs according to volume. Physicians, NPs, residents, and patients belong to the individual, geographical separated practices and do not practice or obtain care at more than one practice. The lack of overlap minimizes the risk of contamination.

Table: Factorial Design Utilized by the Proposed Stepped-Wedge, Cluster-Randomized Trial

Practice	Step 1	Step 2	Step 3	Step 4
A	0	0	1	1+2
B	0	1	1+2	1+2
C	0	2	2	1+2
D	0	0	2	1+2
E	0	1	1	1+2
F	0	2	1+2	1+2

0=Current care  
 1="Less Pain, Less Fuss, Right Now! reminder-recall  
 2="Make It Count!" missed opportunities audit-and-feedback and strong recommendation provider toolkit

**Interventions:** As optimized in Phase 1, the “Less Pain, Less Fuss, Right Now!” intervention consists of a program of reminder-recall communication. For practices randomized to the “Less Pain, Less Fuss, Right Now!” intervention, reminder-recall communication will go out at the beginning of each month. Each month the practice will send a secure electronic communication to the parent or legal guardian of the patient through the patient’s electronic health record portal. We will send mailed letters to parents or guardians of patients who either have opted-out of the portal messaging or who do not access the portal within one week of delivering the reminder-recall through the portal. To support the “Less Pain, Less Fuss, Right Now!” reminder-recall intervention, we will conduct a broad education of the practice staff—nurses, medical secretaries, receptionists, and clinical assistants—regarding the nature of the intervention, its goals, and its likely impact on the practice. The broad education will be conducted through supervisory communications only to practice staff in practices allocated to the intervention at the beginning of the step. As optimized in Phase 2, the “Make It Count!” intervention refers to the two components including the missed opportunities audit-and-feedback and the provision of a strong recommendation provider-toolkit, along with a broad education of the practice staff—nurses, medical secretaries, receptionists, and clinical assistants—regarding the nature of the intervention, its goals, and its likely impact on the practice. The broad education will be conducted through supervisory communications only to practice staff in practices allocated to the intervention at the beginning of the step.

**Data Collection:** For each 12-month period, we will collect patient empaneled data for each participating practice in our region. Demographic and geographic data (including ethnicity, race, sex, age, insurance, street addresses and ZIP codes) will be obtained electronically for all empaneled patients ages 11-12. Our administrative database will be searched electronically to identify the occurrence and dates of all HPV vaccination of children ages 11-12 in our entire system from January 1, 2006, to the end of the study using current procedural terminology (CPT) codes (90649, 90650 and 90651 ). Vaccinations prior to the study period will be used to identify patients who have previously completed 1, 2 or 3 HPV vaccine doses with appropriate spacing (defined according to ACIP recommendations).

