### Endpoints

Our outcome variables are the rates of HPV-vaccine receipt for empaneled eligible males and females, measured at the end of the last day of each 12-month step. Furthermore, eligible individuals must be due for a dose of an HPV vaccine at the start of the 12-month-long step. They could be due for the first, second, or third dose. Eligibility for a dose depends on previously received valid doses received before the beginning of the 12-month-long step. Eligibility also depends upon the amount of time that passed between the last received valid dose and the start of the 12-month-long step. Valid doses include doses given at nine years or older (the minimum age permitted by the ACIP) and meet the minimum intervals. If the individual has received no valid doses previously at age 11 or 12, then the individual is eligible for a first dose. If the individual has previously received one valid dose, and at least 5 months has passed since that dose before the start of the 12-month-long step, then the individual is eligible for a second dose. If the individual has previously received two valid doses but the second dose was given less than 5 months from the first and at least 12 weeks have passed since the second dose and 24 weeks since the first dose, both before the start of the 12-month-long step, then the individual is eligible for a third dose.

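### HPV doses are to be found only through CPT codes in the system's own database, while the aims concern any valid dose; doses given outside the system would be misclassified, by an unknown amount

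*Protocol*

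**What the plan says.** The protocol describes its vaccination data in one place, Data Collection under Study Design and Methods: "Our administrative database will be searched electronically to identify the occurrence and dates of all HPV vaccination of children ages 11-12". The search runs "in our entire system from January 1, 2006, to the end of the study using current procedural terminology (CPT) codes", and three codes are listed (90649, 90650, 90651). The next sentence deals with dose history: "Vaccinations prior to the study period will be used to identify patients who have previously completed 1, 2 or 3 HPV vaccine doses". It names no further source. Nothing in the protocol or SAP mentions a registry, outside records, historical entries or parent report.

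The target of measurement is wider. Aims 1 and 2 each say that the intervention "will improve the odds of a child receiving an HPV vaccine dose by at least 20" per cent. SAP Endpoints states: "Our outcome variables are the rates of HPV-vaccine receipt for empaneled eligible males and females". On eligibility it adds: "Eligibility for a dose depends on previously received valid doses received before the beginning of the 12-month-long step". Validity is set by age and spacing: "Valid doses include doses given at nine years or older (the minimum age permitted by the ACIP) and meet the minimum intervals". The protocol's Inclusion Criteria take the same approach. None of these definitions depends on where the dose was given.

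**The concern.** The estimand is receipt of a valid dose, and the measurement is receipt of a dose that one health system coded. The two differ for any child vaccinated outside the system, whether before joining a practice or during a step. There are two kinds of error.

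- **Outcome.** A dose given outside during a step is scored as a failure.
- **Eligibility.** A child who completed the series elsewhere enters the denominator as due and would normally contribute only a failure. A child with a partial outside history may be given the wrong dose number or wrongly classed as due. Searching back to 2006 does not help, because the search is still within the system.

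Randomization does not protect against capture that the intervention itself changes. Intervention 1 is a message from the practice that features "the convenience of nurse-only visits". If it moves doses from outside the system into it, the recorded rate rises with no extra child vaccinated. If it prompts a family to have the dose outside, a success is recorded as a failure. The target in Aims 1 and 2 is an OR of only 1.20, so a modest artefact matters.

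**Working it through.** **Inputs.** Target OR 1.20 (Protocol, Aims 1 and 2). Baseline probability 25%, 800 children per practice and step, random-effect SD 0.5 (SAP, Power Statement). The SAP calls the 25% a probability of requiring vaccination; I use it as the recorded receipt rate under current care, which is an assumption. The outside share s and the fraction r of outside doses that moves into the system are not in the documents and are varied.

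**1. The plan's own figure.** The documents give no outside-dose figure to reproduce. I first checked that the stated power could be matched, so that the same model could be used in step 5. I used asymptotic power for a mixed logistic model on the protocol's allocation table (6 practices, 4 steps), with categorical step effects, individual ORs of 1.28, and two-sided alpha 0.05 (assumed, as none is stated), averaged over 200 draws of the practice effects. Power is Φ(ln OR / SE − 1.96).

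- Interaction OR 1.34, 800 per practice-step: 80.8% (stated: at least 80%).
- Interaction OR 1.5, 400 per practice-step: 79.4% (stated: at least 80%).
- Interaction OR 1.45, 400 per practice-step: 72.2% (stated: 70%).

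The match is close. It says nothing either way about ascertainment.

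**2. Equal under-capture, no shift of site.** True control rate T = 0.25/(1 − s). Apply a true OR of 1.20 to get T1, then record T1(1 − s).

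- s = 10%: T = 0.2778, T1 = 0.3158, recorded 0.2842. Recorded OR = (0.2842/0.7158)/(0.25/0.75) = 1.19.
- s = 20%: T = 0.3125, T1 = 0.3529, recorded 0.2824. Recorded OR = 1.18.

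The same algebra applies if 10% or 20% of the denominator had already completed the series elsewhere and receive no further dose: 1.19 and 1.18.

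**3. Shift of site under intervention 1, no true effect.** Recorded control rate = 0.25. Recorded intervention rate = T(1 − s(1 − r)).

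| Outside share s | True rate T | Recorded OR, half shift | Recorded OR, all shift |
|---|---|---|---|
| 5% | 0.2632 | 1.04 | 1.07 |
| 10% | 0.2778 | 1.08 | 1.15 |
| 12.5% | 0.2857 | 1.10 | 1.20 |
| 20% | 0.3125 | 1.17 | 1.36 |

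Example, s = 10%, half shift: 0.2778 × 0.95 = 0.2639, and (0.2639/0.7361)/(0.25/0.75) = 1.08. With complete capture every entry would be 1.00.

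**4. Threshold.** A recorded OR of 1.20 needs odds of 1.20 × 0.3333 = 0.40, a rate of 0.2857, which is 3.6 points above 25%. With all outside doses shifting, 0.25/(1 − s) = 0.2857 gives s = 12.5%. Below that share the artefact alone cannot reach the target.

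**5. Chance of a false claim.** In the step 1 model with 800 per practice-step, the SE for intervention 1's ln OR averages about 0.091. An artefactual OR of 1.10 gives 0.0953/0.091 − 1.96 = −0.91, so about 18% of trials would be significant. For 1.15 and 1.20 the figures are about 34% and 52%.

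**The case against.** The strongest reply is that few doses are likely to be given outside. The protocol's background says that adolescent vaccination in the US rests on primary care practices. Its preliminary-data section describes a 7-county area with enough coverage for population estimates. Its Allocation paragraph says that patients do not obtain care at more than one practice. This stands as a reason to expect a modest share. It does not make the share zero: the Allocation statement is about contamination between practices, and the coverage statement is about population estimates.

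It is also fair that the single source is inferred from silence, and that the documents do not say whether outside doses entered in a child's record would carry these codes. If outside doses are already captured, a sentence saying so would settle the point.

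Three stronger readings are tempting, and the documents do not support them.

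- A reader might infer that any move towards practice nurse visits inflates the result. The search is system-wide, so a dose moved from another in-system site is counted either way; only doses from outside the system matter.
- A reader might extend the inflation to Aim 2. No route is described by which the provider audit-and-feedback would change where a dose is given. A shift caused by intervention 1 would also occur under the combination, so it would fall mainly on the intervention 1 term and not on the interaction.
- A reader might infer that every child vaccinated outside is carried forward as still due. That can happen only to children still aged 11 to 12 on the next step's first day, and a child given a first dose elsewhere may by then be genuinely due for a second. The error is then in the dose number.

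**Conclusion.** The concern holds in a limited form. As written, the measurement does not match the aims, and doses given outside the system would be misclassified in both eligibility and outcome. If capture is equally incomplete in all conditions, the cost is slight dilution. Differential error is plausible for intervention 1, alone or combined, and can go in either direction.

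The size is unknown because the documents give no outside-dose rate. The inflation figures assume a recorded control rate of 25%, no true effect, and half to all of outside doses shifting. A reader might infer that intervention 1 could meet its 20% target on artefact alone. That would need at least 12.5% of doses to be outside and, at exactly that share, every one of them to shift; the documents offer no evidence for this. A smaller shift could still add to a real effect. The plan should be changed because the remedy is cheap, not because a large bias has been shown.

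**What to change.** In the protocol's Data Collection paragraph, and by reference in SAP Endpoints, define prior doses and in-step receipt as any valid HPV dose in the child's immunization record, including historical and outside-entered doses. Add an immunization registry if the practices have access to one; the documents do not say whether they do. Keep the CPT codes as one input. Apply the definition to all four steps, so that the baseline and intervention periods are measured alike. Report the share of doses given outside the system by condition, and keep the CPT-only outcome as a sensitivity analysis.

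The cost is a wider electronic data pull, a registry query or linkage where one is possible, and a wording change, with no patient contact. The baseline rate and the number of children due may have to be restated.
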